8 ADVERSE EVENTS

An Adverse Event (AE) is defined as any unfavourable or unintended sign (including an abnormal finding), symptom or disease temporarily associated with the use of a study device whether or not related to the study device. All ocular AEs and related (to the study device and/or to the study procedures) non-ocular AEs, will be monitored and reported on throughout the study.

The Investigator will be required to judge whether or not an AE is device-related. Re-occurring device-related events from the same subject are usually tabulated as separate events. In the case where more than one diagnostic finding is associated with an AE, the event will be counted as one event and categorized under the most significant of the findings.

The Investigator will be required to report all AEs to the study CRO and also to their REC/IRB as required by the REC/IRB guidelines. The seriousness of an AE is categorized as being serious, significant, or non-significant (see Table 3).

Serious	Significant	Non-significant
Results in, or have the potential to cause either permanent impairment of a body function or damage to a body structure and may necessitate medical or surgical intervention. They include but are not limited to:	Symptomatic and warrant discontinuation of contact lens wear (temporary or permanent). They include but are not limited to:	Usually asymptomatic and do not warrant discontinuation of contact lens wear (temporary or permanent). However, as a precautionary measure the Investigator may decide to take action. They include but are not limited to:
MK – Microbial keratitis Permanent reduction in best spectacle-corrected visual acuity (≥ 2 lines) Central (4mm) corneal opacity Central corneal neovascularization Uveitis Iritis Endophthalmitis Hypopyon Hyphema Penetration of Bowman's membrane Persistent epithelial defect Limbal cell damage leading to conjunctivalisation Any untoward medical occurrence that results in death, is life-threatening, requires hospitalization or prolongation of existing hospitalization, results in persistent or significant	CLPU – Contact lens peripheral ulcer CLARE – Contact lens associated red eye SIE – Significant infiltrative event SEAL – Superior epithelial arcuate lesion Corneal warpage SLK – Superior limbic keratoconjunctivitis Other significant ≥grade 3 corneal findings (e.g. edema or abrasions) Any corneal event which necessitates lens wear discontinuation of > 2 weeks Non-CL related anterior segment events e.g. EKC – epidemic keratoconjunctivitis Temporary loss of ≥ 2 lines of best spectacle-corrected visual acuity	CLPC – Contact lens associated papillary conjunctivitis SPK – Superficial punctate keratitis Non-significant infiltrative event Blepharitis Meibomitis Contact dermatitis Localized allergic reactions, including solution-related ocular toxicity Conjunctivitis: Bacterial, Viral, Allergic Keratoconjunctivitis Any corneal event not explicitly defined as a serious or significant event which necessitates lens wear discontinuation <2 weeks Other slit lamp findings requiring treatment
in persistent or significant disability/incapacity or is a congenital anomaly/birth defect	New corneal scar without positive history	

Table 3: Adverse Events by Severity

For additional information, questions, or assistance in recording potential AEs, contact VCR.

8.1 Adverse Event Categorization

The Investigator will be required to rate the likelihood of an event being device-related (Possible, Probable, Highly Probable) or non-device-related (unlikely, definitely not) in their AE evaluation.

All device-related AEs will be tabulated and reported in the final report.

8.2 Adverse Event Reporting

On finding an AE the Investigator will complete an Adverse Event form (AE form) in EDC to capture the event.

The Investigator must notify Visioncare Research of the AE, so that they are able to provide advice and support to the Investigator on how to proceed.

The Investigator must do this by providing the information on the AE eCRF as soon as possible and no later than:

- 24 hours from discovery if event is Serious or Significant
- 5 working days from discovery if event is Non-Significant

Once the form is saved, an automatic email will be sent to VCR and the Sponsor to notify them of the event. If the AE form in EDC cannot be completed on the day of discovery of the AE, then the VCR monitor and the Sponsor (via email address) must be contacted to notify them of the AE.

If applicable, VCR will advise the Investigator to notify the REC as per the REC requirements. VCR may notify the REC on behalf of the Investigator.

The Investigator must notify VCR in writing that the AE has been reported to the REC.

8.3 Adverse Event Documentation

Investigators are required to document and follow-up all AEs.

All AEs are documented on an AE form in EDC upon event discovery. For all ocular AEs, one AE form is used per eye. For AEs which are non-ocular but related to the study device or to the study procedures only one AE form needs to be completed in EDC per AE.

8.4 Adverse Event Follow-up

The Investigator will conduct follow-up examinations until the condition:

- Has returned to pre-event status,
- Is considered stabilized
- Or has been satisfactorily explained.

If the subject is referred for medical attention, they will be tracked by the Investigator until the aforementioned conditions are met.

Follow-up data will be collected on an unscheduled visit eCRF and on the AE form in EDC.

The Investigator should use his/her clinical judgement as to whether or not the subject reporting with an AE should continue in the study.

8.4.1 Device Malfunction

A malfunction means the failure of the device to meet its performance specification or otherwise perform as intended. A malfunction is considered reportable to the Sponsor if it would be likely to cause or contribute to a Serious Adverse Event.

The Investigator will be required to report all reportable device malfunctions to the study CRO/Sponsor via the applicable form in the EDC system.

8.4.2 Sponsor Safety Responsibilities

The sponsor will ensure that all participating Investigators are promptly informed of significant new safety information with respect to the study devices as per regulatory requirements.

To comply with this, the sponsor is responsible for promptly advising (in writing, via VCR) all Investigators conducting clinical studies of any incidents of serious or unexpected adverse events/unanticipated adverse device effects reported for the devices/products involved in those studies.

8.5 Study Completion

The study is completed when all subjects have completed visit 4 or been discontinued, and have been exited from the study.

9 DATA MANAGEMENT

9.1 Electronic Case Report Forms/Data Collection

The clinical data for this study will be entered by designated study site personnel onto electronic report forms (eCRFs) using the electronic data collection (EDC) system Medrio. Paper questionnaires will be given to subjects to complete.

Medrio is compliant with all relevant aspects of ICH/Good Clinical Practices and 21 CFR Part 11 (Electronic Records & Electronic Signatures) regulations.

9.2 Data Quality Assurance

When eCRFs are reviewed at VCR, they will be subjected to error checking and data queries will be raised electronically via the EDC system for resolution of omissions and discrepancies by the investigator.

Before the final closing of the database, the data will be checked and approved for analysis as per VCR SOPs. This includes checking for missing or erroneous data entries

9.3 Data Entry and Storage

All study data shall be entered into the study eCRFs. Completed subject questionnaires (paper) will be sent to VCR on a regular basis and data from the questionnaires will be hand entered into a database using DaCS software and then exported to an Excel database (Microsoft).

All statistical analyses will be completed by VCR using SAS software (SAS Institute Inc., Version 9.4 or later).

10 SAMPLE SIZE AND STATISTICAL METHODS

10.1 Sample Size Rationale

All eligible subjects that complete the MIST-401 Part 2 study will be invited to continue in this study. No new subjects will be enrolled. Based on the current study, there will be approximately 90 subjects completing the study: 44 with six years of MiSight experience (Group T6; original test group in Part 1) and 46 with three years of MiSight experience (Group T3; original control group in Part 1).

Primary Hypothesis

From the MIST-401 Part 1 study, the standard deviations for the paired mean difference and the 2-sample means were estimated. From these the sample sizes of 44 in group T6 and 46 in group T3 will provide at least 99% power to detect non-inferiority.

	Spherical Equivalent Refractive Error (D)		Axial Length (mm)	
	T3:	T6:	T3:	T6:
Hypothesis	Mean progression after 1-year cessation vs. "T3 Baseline" (Control group mean progression Y1-3)			
Test	Non-inferiority Paired (H₀: δ ≤ NIM)	Non-inferiority 2-sample (H₀: δ ≤ NIM)	Non-inferiority Paired (H₀: δ ≤ NIM)	Non-inferiority 2-sample (H₀: δ ≤ NIM)
Alpha	5% (1-sided)	5% (1-sided)	5% (1-sided)	5% (1-sided)
Sample Size	46	44	46	44
Expected Mean Difference	0.00D	0.00D	0.0 mm	0.0 mm
SD of mean or mean difference (σ)	0.36D	0.20D	0.10 mm	0.10 mm
Non-inferiority Margin (NIM)	0.25D	0.25D	0.1mm	0.1mm
Power	100%	100%	100%	99%

N.B. Calculations performed using Hintze, J. (2013). PASS 12. NCSS, LLC. Kaysville, Utah, USA. www.ncss.com.

10.2 Primary End-points

The first primary outcome measure for progression of myopia is defined as the magnitude of change in the spherical equivalent refractive error. Cycloplegic autorefraction was selected to measure refractive error because of its accuracy, repeatability and objectivity, allowing for standardisation of measurements over time and within and across study centres. The spherocylindrical autorefractions will be recorded for each of 5 autorefraction measurements per eye after eliminating sphere or cylinder readings that are more than 1.00D from the mode, and the remaining readings averaged.

The second primary outcome measure is defined as the magnitude of change in axial length, as the progression of myopia has been shown to be associated with increases in axial length. Partial coherence interferometry will be used to measure axial length (mean of 5 readings) as it allows for non-contact measurements with better repeatability compared to conventional ultrasonography.

10.3 Statistical Considerations

All statistical analyses will be performed using the SAS software Version 9.4 or later (SAS Institute, Cary, NC). All data summaries will be performed using Microsoft Excel 2013 or later.

The final analysis will be completed after all subjects have been exited from the study, all queries have been resolved, and the database has been locked.

The mean annual myopic progression will be calculated by dividing the myopic progression for the years in question by the number of years for each subject.

The overall type I error rate will be preserved at 5%. The co-primary hypotheses will be simultaneously evaluated using α =0.05.

Data from unscheduled visits will not be included in the analysis.

10.4 Analysis Population

The statistical analysis for efficacy hypothesis testing will be performed as follows:

- 1. All available data this will include all data from subjects that have completed followup visits. Counts of missing data will be included in the summary statistics.
- 2. Intent-to-treat this will include any subject that has completed at least the 6-month visit. Missing data for 12-month myopia progression and axial length will be extrapolated, where possible, from the 6-month data for the intent-to-treat analysis.

10.5 Descriptive Statistics

Descriptive statistics will be reported at dispensing and each follow-up visit. Continuous variables will be summarized using mean, standard deviation, and range; and categorical data variables will be summarized using percent frequency distribution, mean, and SD. Nominal variables will be summarized using percentages.

Summaries will be presented by group (T3: 3 years of MiSight wear and T6: 6 years of MiSight wear.

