All subjects enrolled should be accounted for, even if they are not dispensed lenses. After enrolment, a subject is considered active and should be accounted for at every visit until the completion of, or discontinuation from the study.

Some baseline data for MIST-402 may include measurements already collected at the final visit for MIST-401 Part 2 (see table below). These measurements do not need to be repeated and the information can be taken from that final visit CRF as long as within a week from enrollment in MIST-402.

The following Screening/Baseline procedures will be conducted on all subjects once enrolled i.e. after the consent/assent (where applicable) documents have been fully executed:

Number	Assessment	Procedure	Instructions and gradings
1	Subject Demographics	Record age, sex and ethnicity	

Number	Assessment	Procedure	Instructions and gradings
2	Medical History	Record medications and associated medical history (such as allergies etc)	
3	Previous Study Lens Wearing Time*	Record the typical insertion & removal times, number of hours worn today, number of days worn per week.	Appendix A – Subjective Assessments
4			
5			
6	Entrance Distance VA	Record the Monocular high contrast distance VA with habitual correction	Appendix A - Visual Acuity and Refraction
7			
8			
10	Manifest Subjective Refraction*	Record the subject's manifest refraction, recording all cylinder in the minus cylinder convention.	Appendix A - Visual Acuity and Refraction
11	BCDVA*	With the manifest refraction record the best corrected distance VA	Appendix A - Visual Acuity and Refraction
12			
13			

Number	Assessment	Procedure	Instructions and gradings
14	Cycloplegia (only if not taking the information from MIST-401 study)	Induce Cycloplegia according to the instructions provided and wait for 25 minutes before conducting cycloplegic assessments.	Appendix A - Cycloplegia
15			
16	Cycloplegic Auto Refraction*	For the auto-refraction measurements the average of the 5 measurements should be recorded on the eCRF after eliminating sphere or cylinder readings that are more than 1.00D from the mode.	Appendix A - Visual Acuity and Refraction
17	Axial Length*	For the axial length measurements, the average of the 5 measurements should be recorded on the eCRF.	Appendix A - Ocular Characteristics
18			
19			

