7.2.6 Visit 4: 12-month Follow-Up

The 12-month follow-up visit will be scheduled 12-months (316-404 days) from Visit 1. The subject should wear the study lenses to the appointment.

Number	Assessment	Procedure	Instructions and gradings
1	Concomitant Medications and Medical History Review	Record any changes to concomitant medications or medical history and confirm if the changes are Adverse events	
2			
3			
4			
5			
6			
7	Entrance Distance VA	Record the Monocular high contrast distance VA with study contact lenses	Appendix A - Visual Acuity and Refraction
8			
9	Spherical Over Refraction	With the contact lenses in record the spherical over refraction	Appendix A - Visual Acuity and Refraction
10	DVA with CLs and Over Refraction	With the contact lenses in and spherical over refraction record the best corrected distance VA	Appendix A - Visual Acuity and Refraction
11			
12			
13			
14			

The following clinical test variables will be recorded on the Follow-Up Visit eCRF:

Number	Assessment	Procedure	Instructions and gradings
15			
16			
17			
18			
19			
20	Cycloplegia	Induce Cycloplegia according to the instructions provided and wait for 25 minutes before conducting cycloplegic assessments.	Appendix A – Cycloplegia
21			
22	Cycloplegic Auto Refraction	For the auto-refraction measurements the average of the 5 measurements should be recorded on the eCRF after eliminating sphere or cylinder readings that are more than 1.00D from the mode.	Appendix A - Visual Acuity and Refraction
23	Axial Length	For the axial length measurements, the average of the 5 measurements should be recorded on the eCRF.	Appendix A - Ocular Characteristics
24			

Number	Assessment	Procedure	Instructions and gradings
25			
26	Instructions	 Subject should be given enough lenses to last until the next visit. Subject will be instructed to wear the lenses for at least 6 days per week and at least 10 hours per day All unused study lenses will be collected from any subjects that were randomised to the Proclear 1- day contact lenses and retained at site until the Close out visit, unless otherwise instructed by VCR or the Sponsor 	

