7.2.7 Study Exit

The Study Exit eCRF must be completed when a subject exits the study. This will occur either at study completion, i.e. after Visit 4, or if the subject is discontinued from the study at another time. A Study Exit eCRF must be completed for all subjects who have a fully executed consent form. The exit date should also be recorded on the subjects named patient notes i.e. the Source Document Record. Post-study follow-up visits will be scheduled if the Investigator judges this is necessary. In this case the Exit eCRF will not be completed until all post-study visits have been completed.

At the study Exit Visit the following measurements are taken and recorded on the Exit eCRF:

Number	Assessment	Procedure	Instructions and gradings
1	Manifest Subjective Refraction	Record the subject's manifest refraction, recording all cylinder in the minus cylinder convention.	Appendix A - Visual Acuity and Refraction
2	BCDVA	If the VA at the Exit Visit is two or more lines worse than at Baseline, the Investigator will be required to provide an explanation and complete an adverse event eCRF	Appendix A - Visual Acuity and Refraction
3			
4	Subject Study Exit	Record if the subject has successfully completed the study. If the subject is being exited due to discontinuation, further details need to be recorded on the exit form. This is described in Section 7.4.	

7.3 Clinical Variables

Table 2 summarises the clinical measurements to be taken at each visit.

The Baseline visit for MIST-402 is expected to be on the same day as MIST-401 Part 2 Exit Visit and will take place straight after the visit.

The MIST-402 Exit Visit will ordinarily take place immediately following Visit 4, but may take place earlier if a subject discontinues from the study. Slit lamp assessment to be performed if Exit Visit does not take place immediately after a follow-up visit.

	BASELINE	DISPENSE		FOLLOW UP VISITS			
PROCEDURES		Day 0	2 wk	6 Mo	12 Mo	UN- SCHED	Exit
Informed Consent and Assent	x						
Demographics	X						
Med History	X						
	X *		X	x	x		
Concomitant medications review	x		X	x	x	x	
Lensometry	X*				X		
Entrance VA	X		Х	X	X	X	
		X	Х	X	X		
	Х*						
	X*				X		Х+
	X*				х		Х+
)	x				х		
	X		X	X	X	X	
)		x	х	X	X		
Contact lens over-refraction		X	Х	X	X		
		X	X	X	X		
	X*			X	X		
Cycloplegic auto-refraction	X*			X	X		
Cycloplegic biometry (axial length)	Х*			x	x		
	X*				X		
				X	X		
Exit VA			Х	X	X		Х+
Dispense study lenses		X	Х	X			

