10.7 Primary Statistical Analysis

T3 Group: The mean myopic progression after cessation of MiSight wear will be compared to the mean annual progression for the first three years (MIST-401 Part 1) for this same group of subjects ("T3 Baseline") on a pairwise basis using linear mixed models. The model will include part, site, and the interaction of site-by-part as fixed effects and subject (nested in site) and eye as random effects. The fixed covariates: subject age group, sex, ethnicity, and baseline myopia (refractive error or axial length) may also be included. If there are convergence issues with the model some or all the covariates may be removed as required.

Statistical non-inferiority will be concluded if the 95% confidence limit of the mean difference of the progression rate after cessation compared to the T3 Baseline rate is greater than -0.25D/year for spherical equivalent refractive error or less than +0.1mm/year for axial length.

T6 Group: The mean myopic progression after cessation of MiSight wear will also be compared to the T3 Baseline mean annual progression using a linear mixed model. The model will include group (T6 or T3), site, and the interaction of site-by-group as fixed effects and subject (nested in site) and eye as random effects. The fixed covariates: subject age group, sex, ethnicity, and baseline myopia (refractive error or axial length) may also be included. If there are convergence issues with the model, some or all the covariates may be removed as required.

Statistical non-inferiority will be concluded if the 95% confidence limit of the mean difference of the progression rate after cessation compared to the T3 Baseline rate is greater than -0.25D/year for spherical equivalent refractive error or less than +0.1mm/year for axial length.

10.8 Secondary Statistical Analysis

The myopic progression after cessation of MiSight wear will be compared to the mean annual myopic progression for previous 3 year's MiSight treatment (MIST-401 – Part 2) on a pairwise basis using linear mixed models. The model will include treatment, site, years of MiSight wear (T6 or T3), and the interaction of site-by-treatment as fixed effects and subject (nested in site) and eye as random effects. The fixed covariates: subject age group, sex, ethnicity, and baseline myopia (refractive error or axial length) may also be included. If there are convergence issues with the model some or all the covariates may be removed as required.

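### Must Section 10.3 say whether the number of years is nominal or elapsed time, given per-year margins and a Visit 4 window of day 316 to 404?

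*Combined protocol and SAP*

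**What the plan says.** Section 10.3 defines mean annual progression as "calculated by dividing the myopic progression for the years in question by the number of years for each subject". It gives no year length and no start or end date.

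For group T3, Section 10.7 states: "The mean myopic progression after cessation of MiSight wear will be compared to the mean annual progression for the first three years". Its decision rule then concerns "the mean difference of the progression rate after cessation compared to the T3 Baseline rate", with limits "greater than -0.25D/year for spherical equivalent refractive error or less than +0.1mm/year for axial length". The T6 comparison uses the same limits. Section 3.3 gives the same margins without a time unit.

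On timing, Section 7.2.6 states: "The 12-month follow-up visit will be scheduled 12-months (316-404 days) from Visit 1". Section 7.2.1 gives the same window as 360 ± 44 days. Section 7.3 adds: "The Baseline visit for MIST-402 is expected to be on the same day as MIST-401 Part 2 Exit Visit". Under Section 7.2.2, previously collected baseline values may be reused: "the information can be taken from that final visit CRF as long as within a week from enrollment in MIST-402".

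For the intent-to-treat set, Section 10.4 states: "Missing data for 12-month myopia progression and axial length will be extrapolated, where possible, from the 6-month data". No time scale is given there either.

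Two other places lean towards nominal time. The table in Section 10.1 describes the comparison as progression over one year of cessation against control progression over years 1 to 3. Section 10.2 defines both primary endpoints as a magnitude of change, not a rate. Neither settles the point.

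**The concern.** A per-year margin calls for a per-year estimate. If the post-cessation change is used as it stands (divided by a nominal 1), a subject seen on day 316 contributes 0.865 of a year's progression and one seen on day 404 contributes 1.106. The window is centred on day 360, slightly short of a calendar year, so even perfect attendance understates the yearly rate a little. In a non-inferiority comparison that error favours the claim. If attendance also drifted early, the bias would grow.

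Section 10.7 adds to the doubt by setting a progression against an annual progression and then calling the first a rate. Two statisticians could follow the text faithfully and report slightly different primary estimates. The study is open label with a comparator from an earlier study, so a time scale chosen after the data are seen is a freedom one would rather not leave. At stake is the promise in Section 10.3 to hold type I error at 5%.

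**Working it through.** **Inputs from the documents.** Section 10.1: one-sided alpha 5%; n = 46 (T3, paired) and 44 against 46 (T6, two-sample); SDs for SERE 0.36 D (T3) and 0.20 D (T6), for AL 0.10 mm in both; margins 0.25 D and 0.1 mm; expected difference zero. Sections 7.2.1 and 7.2.6: Visit 4 on day 316 to 404, centre 360.

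**Assumed.** The documents give no control progression rate. I use 0.40 D/year (range 0.3 to 0.6) and 0.20 mm/year (range 0.15 to 0.25). For T6 the SD is taken as common to both groups. A year is 365.25 days. Progression is written as a magnitude, so larger is worse.

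**Step 1: reproduce the stated power.** Noncentral t, with these standard errors:
- T3: 0.36/√46 = 0.0531 D and 0.10/√46 = 0.0147 mm, 45 df.
- T6: 0.20 × √(1/44 + 1/46) = 0.0422 D and 0.10 × √(1/44 + 1/46) = 0.0211 mm, 88 df.

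Power at zero difference is 99.86% (T3 SERE), above 99.99% (T6 SERE), above 99.99% (T3 AL) and 99.89% (T6 AL). The plan states 100%, 100%, 100% and 99%, so its figures are reproduced within rounding or slightly exceeded.

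**Step 2: elapsed-time reading.** Each change is divided by days/365.25. The estimate is then on the margin's own scale and there is nothing to correct.

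**Step 3: nominal reading, shift in the mean.** With visits centred on day 360 the shortfall is 5.25/365.25 = 1.44%.
- SERE: 0.40 × 0.0144 = 0.0057 D, which is 2.3% of 0.25 D.
- AL: 0.20 × 0.0144 = 0.0029 mm, which is 2.9% of 0.1 mm.

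Spreading visits uniformly over the whole window raises the T3 SERE SD only from 0.360 to 0.361.

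**Step 4: nominal reading, one-sided error when the true excess equals the margin.** With f = mean days/365.25, the observed excess is (ref + margin) × f − ref × g. Here g is the length of a Part 1 year in true years: 360/365.25 if Part 1 visits also ran to a 360-day year, or 1 if Part 1 was annualised exactly. At day 360 with g = 360/365.25 the reference rate cancels, leaving 0.25 × 0.9856 = 0.2464 D and 0.1 × 0.9856 = 0.0986 mm.

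| Mean Visit 4 day | Part 1 year | T3 SERE | T3 AL | T6 SERE | T6 AL |
|---|---|---|---|---|---|
| 360 | 360 days | 5.7% | 6.1% | 5.9% | 5.7% |
| 360 | 365.25 days | 7.1% | 8.7% | 7.7% | 7.5% |
| 367 (every baseline a week old) | 365.25 days | 4.4% | 4.1% | 4.3% | 4.3% |
| 350 (early drift) | 360 days | 10.6% | 15.9% | 12.7% | 11.7% |
| 350 (early drift) | 365.25 days | 12.7% | 21.0% | 15.7% | 14.6% |

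At a mean of exactly 365.25 days with exact Part 1 years, all four are 5.0%.

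**Step 5: power with late attendance.** With every visit on day 404, nominal time and exact Part 1 years, power at zero difference is 98.6%, above 99.9%, 99.9% and 98.0% in the same order. At the top of the assumed rates (0.60 D/year and 0.25 mm/year) the lowest value is 96.5%.

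**The case for a change.** The strongest reply is that the low figures, 5.7% to 6.1%, assume Part 1 ran to the same short year. Part 1 visit dates are not in the documents. If those visits fell on exact three-year anniversaries, dividing by a nominal 3 equals exact annualisation, and the error at the margin is 7.1% to 8.7% with no change of rule between periods. A mean Visit 4 only ten days early would then give 12.7% to 21.0%. Out-of-window visits can also be accepted as scheduled by agreement (Section 7.2.1), so elapsed time is not strictly bounded. Writing the definition down would cost a sentence.

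The arithmetic stands, and so does the point about Part 1 dates. The figures have limits, however:
- They are error rates at one point, a true excess exactly at the margin. Section 10.1 plans for zero difference, where the nominal shift is 2% to 3% of the margin.
- The window is symmetric about day 360 and nothing in the documents suggests early attendance. Late attendance and reused week-old baselines push the error the other way.
- The T6 SERE figures lean on a common SD of 0.20 D. The paired T3 SD of 0.36 D exceeds 0.20 × √2 = 0.283 D, so the cessation-year SD may well be larger. A larger SD makes the inflation smaller.
- Section 10.3 calls SERE and AL co-primary. If both must pass, which the text does not say outright, the joint error cannot exceed the smaller of the two: in T3, 7.1% at day 360.

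The 6-month extrapolation is a separate gap in method. If it simply doubled the change, a visit on day 166 to 194 would stand for day 332 to 388, which lies inside the Visit 4 window. It affects only subjects who have a 6-month visit and no 12-month visit.

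**Conclusion.** The plan leaves a definition unwritten, but either reading gives a sound primary analysis. Elapsed time matches the per-year margins exactly. Nominal time, which Sections 10.1 and 10.2 lean towards, shifts the mean by about 0.006 D or 0.003 mm with visits centred on day 360. Error at the margin is then 5.7% to 6.1% if Part 1 ran to a 360-day year, or 7.1% to 8.7% if it ran to exact anniversaries. Power at the planned zero difference is hardly touched.

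This rests on assumed control rates of 0.40 D/year and 0.20 mm/year, the SDs in Section 10.1, and attendance roughly centred in the window. Systematic early attendance would matter, but it is hypothetical and would show in the visit dates. An analyst would ordinarily fix the year definition when programming the analysis and apply one rule to Part 1, Part 2 and MIST-402. The gain from amending the plan is negligible, so no change follows.
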